- To explore the effects of SEP-363856 and quetiapine XR on functional capacity as measured by the University of California San Diego (UCSD) Performance-Based Skills Assessment – Brief Version (UPSA-B)
- To evaluate the effects of SEP-363856 and quetiapine XR on function as measured by the modified Specific Level of Functioning Scale (SLOF)
- To evaluate the effects of SEP-363856 and quetiapine XR on health-related quality of life as measured by the EuroQol-5D-5L (EQ-5D-5L)
- To evaluate medication satisfaction as measured by the Medication Satisfaction Questionnaire (MSQ)
- To explore the impact of SEP-363856 on nicotine use

CCI

Study Design:

This is a 52-week, multicenter, randomized, double-blind, parallel-group, flexible-dose study designed to evaluate the long-term safety and tolerability of SEP-363856 (50 to 100 mg/day) in clinically stable adults with schizophrenia. This study is projected to randomize approximately 300 subjects to two treatment groups (SEP-363856 50 to 100 mg/day or quetiapine XR 400 to 800 mg/day) in a 2:1 ratio. Study drug will be taken at the same time each evening at bedtime and should be taken without food or with a light meal.

A Data and Safety Monitoring Board (DSMB) will review safety data approximately every 6 months during the study. The DSMB will be independent of the Sponsor, study contract research organization (CRO) and the Investigators and will be empowered to recommend stopping the study due to safety concerns. The membership of the DSMB and its mandate will be described in a separate DSMB Charter.

The study will consist of three periods: Screening/Washout (up to 21 days), Treatment (52 weeks) and a Follow-up visit (7 days after the last study drug dose).

Screening/Washout Period (up to 21 days):

Informed consent will be obtained from each subject before any study procedures are performed. Subjects will be evaluated for eligibility during a Screening/Washout Period of up to 21 days, during which they will be tapered off all psychotropic medications (except as noted in the Concomitant Medications section below) in a manner that is consistent with labeling recommendations and conventional medical practice. The Screening Period may be extended for up to 7 days after approval from the Medical Monitor.

Subjects may be hospitalized for up to one week prior to randomization during the Screening/Washout Period, if deemed clinically necessary by the Investigator. Additional hospitalization during the

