8.2. Subject Exclusion Criteria

To qualify for participation, subjects must not meet any of the following exclusion criteria:

1. Subject was hospitalized for a psychiatric illness within the 8 weeks prior to Screening.
2. Subject has a current DSM-5 diagnosis or presence of symptoms consistent with a DSM-5 diagnosis other than schizophrenia. Exclusionary disorders include but are not limited to alcohol use disorder (within past 12 months or for a total of ≥ 10 years during the subject's lifetime), substance (other than nicotine or caffeine) use disorder within past 12 months or for a total of ≥ 10 years during the subject's lifetime, major depressive disorder, schizoaffective disorder, bipolar I or II disorder, obsessive compulsive disorder, and posttraumatic stress disorder. Symptoms of mild to moderate mood dysphoria or anxiety are allowed so long as these symptoms are not the primary focus of treatment.
3. Subject is judged to be resistant to antipsychotic treatment by the Investigator, based on failure to respond to 2 or more marketed antipsychotic agents within a 1-year period prior to Screening, given at adequate dose as per labeling, for at least 4 weeks.
4. Subject answers "yes" to "Suicidal Ideation" Item 4 (active suicidal ideation with some intent to act, without specific plan) or Item 5 (active suicidal ideation with specific plan and intent) on the C-SSRS assessment at Screening (i.e., in the past one month) or at Baseline (i.e., since last visit).
5. Subject is at significant risk of harming self or others based on Investigator's judgment.
6. Subject has attempted suicide within 6 months prior to Screening.
7. Subject has received treatment with a psychotropic medication or herbal supplement within 3 days or 5 half-lives (whichever is longer) prior to randomization or anticipates the need for psychotropic medications or herbal supplements during their participation in this study, with the exception of the medications specified in [Section 10.3.5](#). The following medications have additional washout requirements as specified below:
 - Monoamine oxidase inhibitors (MAOIs) must be discontinued at least 28 days prior to randomization.
 - Fluoxetine must be discontinued at least 28 days prior to randomization.

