11.5.11. Healthcare Resource Utilization (HCRU)

HCRU will be assessed by recording the following:

- number of physician office visits, emergency room visits, and hospitalizations (total number and number related to schizophrenia) in the previous 3 months
- length of each hospital stay in the past 3 months
- employment status in the past 3 months
- the average number of hours a caregiver(s) spends helping the subject per week (past 3 months)

11.6.

CCI

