11.7.7. Visit 7 (Week 12; Day 85 ± 3)

The following procedures will be conducted during this visit:

- Concomitant medication review
- Study drug accountability
- Dispense study drug
- Tobacco use information
- Physical and neurological examinations
- Vital signs
- Weight (BMI derived in the EDC system)
- Waist circumference
- Standard 12-lead ECG
- Fasted Blood sample for clinical laboratory tests (hematology and serum chemistry)
- **CCI** [REDACTED]
- Urine sample for urinalysis and urine drug screen (UDS)
- Urine pregnancy test (β -HcG), female subjects only
- Adverse events monitoring
- C-SSRS
- SLOF
- BACS
- UPSA-B
- HCRU

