11.7.10. Visit 10 (Week 24; Day 169 \pm 3)

The following procedures will be conducted during this visit:

- Concomitant medication review
- Study drug accountability
- Dispense study drug
- Tobacco use information
- Physical/neurological examinations
- Vital signs
- Weight (BMI derived in the EDC system)
- Waist circumference
- Standard 12-lead ECG
- Fasted Blood sample for clinical laboratory tests (hematology and serum chemistry)
- **CCI**
- Urine sample for urinalysis and UDS

- Urine pregnancy test (β -HcG), female subjects only
- Adverse events monitoring
- PANSS
- BNSS
- MADRS
- C-SSRS
- CGI-S
- SAS
- BARS
- AIMS
- ESS
- SLOF
- BACS
- UPSA-B
- HCRU

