11.7.13. Visit 13 (Week 36; Day 253 ± 3)

The following procedures will be conducted during this visit:

- Concomitant medication review
- Study drug accountability
- Dispense study drug
- Physical and neurological examinations
- Vital signs
- Weight (BMI derived in the EDC system)
- Waist circumference
- Standard 12-lead ECG
- Fasted Blood sample for clinical laboratory tests (hematology and serum chemistry)
- CCI [REDACTED]
- Urine sample for urinalysis and urine drug screen (UDS)
- Urine pregnancy test (β -HcG), female subjects only
- Adverse events monitoring
- C-SSRS
- HCRU

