17.6.5 HEALTHCARE RESOURCE UTILIZATION

Healthcare resource utilization is assessed at these study visits: Visit 2, Visit 7, Visit 10, Visit 13, and Visit 17.

The frequency and percentage of subjects with physician's office visits, ER visits, and hospitalizations (for any reason and those related to schizophrenia) at Baseline and at each post-Baseline scheduled visit (Week 12/Visit 7, Week 24/Visit 10, Week 36/Visit 13, Week 52/Visit 17) (capturing the information during the past 3 months) will be summarized. The number of physician's office visits, ER visits, and hospitalizations (for any reason and those related to schizophrenia) per month at Baseline and at each post-Baseline scheduled visit (Week 12/Visit 7, Week 24/Visit 10, Week 36/Visit 13, Week 52/Visit 17), as well as the average length of hospital stays (for any reason and those related to schizophrenia) at Baseline and at each post-Baseline scheduled visit (Week 12/Visit 7, Week 24/Visit 10, Week 36/Visit 13, Week 52/Visit 17), will be summarized. The frequency and percentage of subjects receiving unpaid care at each time point, along with the average number of hours a caregiver spends per week helping the subject, will also be summarized.

The change in the number of physician's office visits, ER visits, and hospitalizations per month, the average length of hospital stays, and the average number of hours a caregiver spends per week helping the subject from Baseline at each post-Baseline scheduled visit (Week 12/Visit 7, Week 24/Visit 10, Week 36/Visit 13, Week 52/Visit 17) will be summarized.

Shift from Baseline to each post-Baseline scheduled visit (Week 12/Visit 7, Week 24/Visit 10, Week 36/Visit 13, Week 52/Visit 17) in whether the subjects receive unpaid care will also be summarized.

Document: CCI

Author: PPD

Version Number: 0.6

Version Date: 30JAN2023

Template No.: CS_TP_BS016 Revision 6

Reference: CS_WI_BS005

Effective Date: 02Dec2019

18

CCI

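### The fixed 3-month HCRU recall does not fit the visit schedule, so early-termination forms report mostly or partly pre-dose use as post-Baseline use (minor)

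*Protocol*

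**What the plan says.** Protocol 11.5.11 records the "number of physician office visits, emergency room visits, and hospitalizations (total number and number related to schizophrenia) in the previous 3 months". Length of stay, employment status and caregiver hours carry the same look-back. Neither document gives a different recall for any visit.

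SAP 17.6.5 says that "Healthcare resource utilization is assessed at these study visits: Visit 2, Visit 7, Visit 10, Visit 13, and Visit 17". The visit lists in Protocol 11.7 agree. Visit 17 doubles as the ET visit and includes HCRU (Protocol 11.7.17).

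SAP 6.2 takes Baseline strictly from the Visit 2 form. Under SAP 6.4, an ET record within 9 days of the last dose is assigned to the next visit at which that assessment was due. SAP 6.3 lets the same record supply the LOCF value. SAP 17.6.5 then summarises monthly counts by visit, and also "The change in the number of physician's office visits, ER visits, and hospitalizations per month, the average length of hospital stays" and caregiver hours as change from Baseline. It gives no divisor for the monthly figure and no rule for pre-dose time.

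Two entry rules bear on Baseline. Protocol 8.2 excludes a person if "Subject was hospitalized for a psychiatric illness within the 8 weeks prior to Screening". The Synopsis states that "Subjects may be hospitalized for up to one week prior to randomization during the Screening/Washout Period", if clinically necessary.

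Employment status is an HCRU endpoint in SAP 2.2.2, and Protocol 15.3.6.9 says it will be summarised. SAP 17.6.5 contains no such summary, and SAP 3.7 does not list the omission as a change.

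**The concern.** The stated objective is the impact of SEP-363856 on healthcare use (Protocol 5.2). A value labelled Week 12 or LOCF should therefore describe use on treatment. A look-back of fixed length does that only if it is no longer than the time since first dose, and it covers all treatment time only if it is no shorter than the interval between forms. Here it fails the first test at Week 12 and at early ET, and the second at Week 52. ET is the more serious case: the mapping rule gives a post-Baseline label to a record that may describe mainly the months before the trial.

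Baseline raises a separate question. If entry criteria remove most of the time in which a psychiatric admission could have occurred, a within-arm rise may reflect selection at entry and not treatment.

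**Working it through.** The plan gives no figure of its own for this point, so the check is day arithmetic. Inputs:

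- Recall: 3 months, taken as 91 days (89 to 92 by calendar), from Protocol 11.5.11.
- Assessment days: 1, 85, 169, 253 and 365, from the Protocol 11.7 headings: "Visit 7 (Week 12; Day 85 ± 3", "Visit 10 (Week 24; Day 169", "Visit 13 (Week 36; Day 253 ± 3", and Day 365 for Visit 17. These equal 7 × week + 1. Post-Baseline windows are ±3 days.
- Psychiatric-admission exclusion: 8 weeks = 56 days before Screening. Screening lasts up to 21 days, or 28 with the permitted extension.
- Completion: about 80 of 300 × 2/3 = 200 SEP-363856 subjects (Protocol 15.1).

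**Scheduled visits** (recall minus spacing)

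| Interval | Spacing (days) | 91 − spacing |
|---|---|---|
| Day 1 to 85 | 84 | +7 |
| Day 85 to 169 | 84 | +7 |
| Day 169 to 253 | 84 | +7 |
| Day 253 to 365 | 112 | −21 |

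At Week 12 the extra 7 days (5 to 8 for recall of 92 down to 89 days) lie before first dose, in the week when a pre-randomisation stay is permitted. One stay can therefore appear at both Baseline and Week 12. Before Week 52, 21 days are not covered: 20 to 23 over the recall range, 14 to 29 with visit windows. As a share of treatment time, 21/364 = 5.8%.

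**Early termination** (pre-dose days at ET in week *w* = 91 − 7*w*)

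| ET at | Pre-dose days | Share of 91 |
|---|---|---|
| Week 2 | 77 | 85% |
| Week 4 | 63 | 69% |
| Week 6 | 49 | 54% |
| Week 8 | 35 | 38% |

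The share reaches zero at about Day 91. A subject leaving at any of these times has not attended Week 12, so SAP 6.4 reports the record as Week 12.

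To gauge how many are affected, assume a constant dropout hazard, which the documents do not state. Completion is 80/200 = 40%, so hazard = −ln(0.40)/364 = 0.00252 per day. Leaving by Day 91: 1 − exp(−0.00252 × 91) = 20.5%, about 41 of 200. By Day 29 it is about 14, and by Day 57 about 27.

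**Baseline**

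The exclusion closes 56/91 = 62% of the window (61% to 63% over the recall range). The other 35 days are open: 14 before the exclusion period plus 21 of Screening, or 7 plus 28 with the extension. If psychiatric admissions ran at a constant rate on all open days, Baseline would show 35/91 = 38% of that rate. If none occurred during Screening, it would show 14/91 = 15% (21-day Screening) or 7/91 = 8% (28-day Screening).

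**The case against.** The case for leaving the plan alone has several parts.

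- **One scale.** Equal 3-month windows keep Baseline and follow-up comparable. SAP 17.6.5 summarises each visit separately and sums nothing across visits, so the overlap double counts nothing within a visit. This stands for the overlap between on-treatment visits. It does not answer pre-dose use counted as post-Baseline use.
- **The gap.** A reader might infer that admissions in the 21 uncovered days are lost to the trial. The documents do not support that. Hospitalization is an SAE criterion (Protocol 12.1.2), AEs are collected at visits and by telephone between them, and SAP 16.2.12 uses a Psychiatric Hospitalization CRF page with admission dates. What is lost is mainly office visits, ER visits and similar items at one visit.
- **Number affected.** A reader might infer that all of the roughly 120 expected non-completers on SEP-363856 have contaminated records. Pre-dose reach-back affects only ETs before about Day 91, about 41 of 200 under the assumed hazard, and the pre-dose share falls below half after about Week 6.
- **Form not shown.** SAP 17.6.5 analyses an unpaid-care item that Protocol 11.5.11 does not mention, so the protocol may not describe the whole form. The ET wording should be checked against the CRF.
- **The remedy can mislead.** With recall from first dose, one admission before a Week 2 ET becomes 30.4/14 = 2.2 per month, against 1/3 = 0.33 under 3-month recall. Averages of subject-level rates would be dominated by early leavers. This stands and shapes the fix.

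**Conclusion.** The mismatch holds. Its main consequence is that ET records from before about Day 91, 85% pre-dose at Week 2 and 69% at Week 4, enter the Week 12 and LOCF summaries as post-Baseline use. The 7-day reach-back at Week 12 and the 21-day gap before Week 52 are smaller. These figures rest on a 91-day recall and on the ET form using the recall in Protocol 11.5.11. The count of about 41 also rests on a constant hazard.

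Two stronger readings are not supported. One is that entry criteria almost empty the Baseline of schizophrenia admissions, so that change from Baseline is pushed upward whatever the drug does. The exclusion closes 62% of the window, and only a 28-day Screening with no admission in it comes near that description. Permitted washout stays raise Baseline, and ET reach-back pulls follow-up values towards pre-dose levels, so the net direction is not fixed.

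The other is that the comparison between arms, or HCRU change in general, is biased. The exclusion applies equally to both randomised arms and only to psychiatric admissions and their length of stay. It does not touch office visits, non-psychiatric admissions or caregiver hours. ET reach-back would distort the contrast only if ET timing differed between arms, which the documents do not establish.

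Severity is minor: HCRU is an other-safety endpoint, summarised descriptively with no test.

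**What to change.** **Form.** For post-Baseline and ET forms, start the recall at the last HCRU assessment, or at first dose for the first form. C-SSRS already uses a since-last-visit version (Protocol 11.5.10).

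**If the form cannot change.** This is likely, because SAP 3.5 shows enrolment began before the 2020 amendment. In SAP 6.3 and 6.4, do not map ET HCRU records from before about Day 91 to Week 12 or LOCF as on-treatment use; list them separately. Take on-treatment psychiatric admissions from the Psychiatric Hospitalization CRF and SAE dates.

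**SAP 17.6.5.**

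- Report total events over total person-months actually covered, by arm, and not the mean of subject-level rates. If the 3-month form stays, do not sum its counts across overlapping windows; use the dated admissions for totals.
- State the divisor for every monthly figure.
- Add a caution that within-arm change in schizophrenia admissions reflects the entry criteria.
- Restore the employment-status summary specified in Protocol 15.3.6.9.

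**Cost.** The form route is one wording change. It lengthens recall to 16 weeks at Week 52, and follow-up windows no longer equal the 3-month Baseline. The SAP route needs text changes and a derivation from dates already collected. It leaves fewer subjects in the Week 12 and LOCF summaries, and it does not recover office or ER visits in the uncovered days.

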11.7. Study Visits and Assessments

See [Table 2](#) Schedule of Assessments, for a summary of procedures at each study visit.

Unscheduled visits can be conducted during the study at the discretion of the Investigator.

It is suggested that the rating scales be completed in the following order, if possible:

1. PANSS ^a
2. BNSS
3. MADRS
4. C-SSRS
5. SAS/BARS/AIMS
6. SLOF
7. EQ-5D-5L
8. ESS
9. MSQ
10. BACS
11. UPSA-B
12. HCRU
13. CGI-S

a When administering the PANSS, it is suggested that the informant interview and PANSS-IC be completed prior to the subject interview.

Note: With the exception of the SCID-CT, UPSA-B, C-SSRS and the HCRU all rating assessments will be completed by the rater using an electronic tablet. In the event that the electronic tablet is not available, the rating assessments will be performed by the rater or subject using a paper version of the assessment, with the exception of the EQ-5D-5L which is licensed only for electronic use.

11.7.1. Screening: Visit 1 (Day -21 to -1)

After a subject provides consent, a unique subject number will be assigned at screening by the IWRS, consisting of a 3-digit protocol number, 3-digit site number, and a unique 3-digit subject identifier (eg, the second screened subject from site #005 will be 304005002). Subjects will be numbered consecutively. No subject numbers are to be reused once assigned. This number will track a subject throughout their participation in the study.

Subjects will be evaluated at the Screening Visit to determine their eligibility for the study. The subject's eligibility assessment will be reviewed by the contract research organization's (CRO) oversight quality team along with the sponsor based on protocol specified inclusion and exclusion criteria. In the event the CRO/sponsor and site do not agree on a subject's eligibility then the subject will not be enrolled.

Subjects found to be ineligible during Visit 1 will not be required to complete all the Visit 1 assessments and will not be followed upon leaving the study.

Subjects who screen fail may be re-screened once, if judged appropriate by the Investigator, after discussion with the Medical Monitor. Re-screened subjects will be re-consented, assigned a new subject number, and all Visit 1 procedures will be repeated.

The Screening Period may be extended for up to 7 days after approval from the Medical Monitor.

The following procedures will be conducted during this visit:

- Obtain signed informed consent and privacy authorization (if applicable or required by local law) from the subject before conducting any other visit procedures, including informed consent for duplicate subject check (where allowed by local/regional regulations)
- CCI
- Review inclusion and exclusion criteria
- Collect prior and concomitant medications
- Obtain demographic information
- Collect adverse events (Note: events occurring prior to first dose of study drug will be identified programmatically as pretreatment events.)
- Collect medical history
- Collect psychiatric history
- SCID-CT
- Physical and neurological examination
- Height and weight; clinical site staff to calculate and record BMI
- Vital sign measurements
- Standard 12-lead ECG
- Fasted blood samples for clinical laboratory evaluation (hematology and serum chemistry)
- Blood samples for serum pregnancy test (serum human chorionic gonadotropin [β -hCG]) for female subjects of childbearing potential and serum follicle stimulating hormone (FSH) for post-menopausal women or if menopause is suspected.
- Blood sample for hepatitis screening
- Urine sample for urinalysis and urine drug screen (UDS)
- PANSS
- C-SSRS
- CGI-S
- MSQ, only for subjects currently treated with an antipsychotic medication or had been treated with antipsychotic medication within 30 days of screening
- Duplicate subject check (where allowed by local/regional regulations)

11.7.2. Baseline: Visit 2 (Day 1)

The following procedures will be conducted during this visit:

- CCI
- Collect prior/concomitant medications
- Tobacco use information
- Vital sign measurements
- Weight (BMI derived in the EDC system)
- Waist circumference
- Standard 12-lead ECG
- Fasted blood samples for clinical laboratory evaluation (hematology and serum chemistry)
- If subject signed separate genetic informed consent, collect a blood sample for potential pharmacogenomics
- CCI
- Urine sample for urinalysis, UDS, and β -hCG (for female subjects).
- PANSS
- BNSS
- MADRS
- C-SSRS
- CGI-S
- SAS
- BARS
- AIMS
- ESS
- SLOF
- EQ-5D-5L
- BACS
- UPSA-B
- Healthcare resource utilization
- Collect adverse events (Note: events occurring prior to first dose [on Day 1] of study drug will be identified programmatically as pretreatment events.)
- Review inclusion and exclusion criteria

- Randomize to treatment
- Dispense study drug

11.7.3. Visit 3 (Week 1; Day 8 + 2)

The following procedures will be conducted during this visit:

- Concomitant medication review
- Study drug accountability
- Dispense study drug
- Adverse events monitoring
- Vital signs
- Standard 12-lead ECG
- Fasted Blood sample for clinical laboratory tests (hematology and serum chemistry)
- CCI [REDACTED]
- Urine sample for urinalysis and urine drug screen (UDS)
- Urine pregnancy test (β -HcG), female subjects only
- PANSS
- BNSS
- MADRS
- C-SSRS
- CGI-S
- SAS
- BARS
- AIMS

11.7.4. Visit 4 (Week 2; Day 15 \pm 2)

The following procedures will be conducted during this visit:

- Concomitant medication review
- Study drug accountability
- Dispense study drug
- Vital signs
- Urine pregnancy test (β -HcG), female subjects only
- Adverse events monitoring
- C-SSRS

